## 12.2.2 Unexpected Adverse Event

An adverse event or suspected adverse reaction is considered "unexpected" if it is not listed in the current AMG 714 IB or is not listed at the specificity, severity or rate of occurrence that has been observed.

"Unexpected" also refers to adverse events or suspected adverse reactions that are mentioned in the current IB as occurring with a class of drugs or as anticipated from the pharmacological properties of the drug, but are not specifically mentioned as occurring with the particular drug under investigation (21 CFR 312.32(a)).

#### 12.2.3 Serious Adverse Event

An adverse event or suspected adverse reaction is considered "serious" if, in the view of either the investigator or Sponsor (DAIT/NIAID), it results in any of the following outcomes (21 CFR 312.32(a)):

- 1. Death.
- 2. A life-threatening event: An AE or SAR is considered "life-threatening" if, in the view of either the investigator or Sponsor (DAIT/NIAID), its occurrence places the participant at immediate risk of death. It does not include an AE or SAR that, had it occurred in a more severe form, might have caused death.
- 3. Inpatient hospitalization or prolongation of existing hospitalization.
- 4. Persistent or significant incapacity or substantial disruption of the ability to conduct normal life functions.
- 5. Congenital anomaly or birth defect.
- 6. Important medical events that may not result in death, be life threatening, or require hospitalization may be considered serious when, based upon appropriate medical judgment, they may jeopardize the participant and may require medical or surgical intervention to prevent one of the outcomes listed above.

Elective hospitalizations or hospital admissions for the purpose of conduct of protocolmandated procedures are not to be reported as an SAE unless hospitalization is prolonged due to complications.

# 12.2.4 Adverse Events of Special Interest (AESI)

Any occurrence of malignancy will be considered an Adverse Event of Special Interest (AESI) and must be reported to the IND Sponsor within 24 hours, according to the procedure for SAEs described in Section 12.5.1.

#### 12.3 GRADING AND ATTRIBUTION OF ADVERSE EVENTS

#### 12.3.1 Grading of Hypersensitivity and Anaphylaxis

For this study, hypersensitivity and anaphylaxis reactions will be graded according to Table 3 below. The final grade of the reaction will not be determined until the event is over. Any reaction that results in the permanent discontinuation of the AMG 714 (Section 6.4.1) should be reported according to the procedure for SAEs described in Section 12.5.1.

Table 3. Grading of Hypersensitivity and Anaphylaxis Reactions

(Modified from World Allergy Organization Subcutaneous Immunotherapy Systemic Reaction Grading System^50).

Grade 1	Grade 2	Grade 3	Grade 4	Grade 5
Symptom(s)/ sign(s) of one organ system	Symptom(s)/ sign(s) of more than one Grade 1 organ system present or	Lower respiratory  Asthma (e.g., 40% PEF or FEV1 drop, NOT responding to an inhaled bronchodilator)	Lower or Upper respiratory  Respiratory failure with or without loss of consciousness	Death
Angioedema (not laryngeal, tongue or uvular)  or  Upper respiratory  Rhinitis (e.g., sneezing, rhinorrhea, nasal pruritus and/or nasal congestion)  or  Throat-clearing (itchy throat)  or  Cough perceived to come from the upper airway, not the lung, larynx, or trachea  or  Conjunctival  Conjunctival erythema, pruritus or tearing or  Other  Nausea, metallic taste, or headache	Lower respiratory  Asthma: cough, wheezing, shortness of breath (e.g., less than 40% PEF or FEV1 drop, responding to an inhaled bronchodilator)  or  Gastrointestinal  Abdominal cramps, vomiting, or diarrhea  or  Other  Uterine cramps	or  Upper respiratory  Laryngeal, uvula or tongue edema with or without stridor	Cardiovascular Hypotension with or without loss of consciousness	

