### 5. KNOWN AND POTENTIAL RISKS AND BENEFITS TO PARTICIPANTS

# 5.1 RISKS OF INVESTIGATIONAL DRUG AS CITED IN INVESTIGATOR'S BROCHURE

Precautions for hypersensitivity events are required. Hypersensitivity events such as injection site reaction (13.3%), injection site pain (2%), rash (4.7%), and eczema (3.1%) were reported in individuals receiving AMG 714.  All hypersensitivity reactions were mild and transient. There are no reports of anaphylaxis to AMG 714. All individuals who receive AMG 714 or AMG 714 placebo will be monitored for 1 hour after injection to detect any possible injection site reaction, hypersensitivity, and/or anaphylactic reaction (Section 6.1.3.4). AMG 714 is contraindicated in individuals with a known sensitivity to proteins derived from mammalian cell lines or other components of this drug.

The effect of AMG 714 on pregnancy, breast-feeding, pediatric participants, or geriatric participants is not known. No clinical studies have been conducted in individuals with renal or hepatic impairment. The effects of an overdose of AMG 714 are not known, and an antidote is not available. There is no evidence that AMG 714 use is habit forming.

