#### 6.1.3.3 Administration

Temperature, blood pressure, pulse and respirations will be obtained immediately before study drug administration and 60 minutes after study drug administration. Study participants will be monitored for 1 hour after study drug administration to detect any possible injection site reaction, hypersensitivity, and/or anaphylaxis (Section 6.1.3.4).

AMG 714 or placebo will be administered subcutaneously by trained health care staff not otherwise involved in the vitiligo assessment of the participant (Section 3.5.1). Each dose will be comprised of two separate syringes, each containing 1.5 ml of AMG 714 or placebo. The SQ injections should be administered on the participant's anterior abdominal wall in a consecutive fashion approximately 2 cm apart. The side of the abdominal wall should be alternated at every visit (i.e., left side at one visit, right side at the next visit).

If more than one participant is scheduled to receive study drug on the same day at the same investigational site, at least 15 minutes must elapse between study drug administration to each participant.

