#### 12.3.3 Grading Criteria

For all other adverse events not related to hypersensitivity, anaphylaxis or liver chemistry abnormalities, the study site will grade the severity of adverse events experienced by the study participants according to the criteria set forth in the NCI-CTCAE (version 5.0, November 27, 2017). This document (here in referred to as the NCI-CTCAE manual) provides a common language to describe levels of severity, to analyze and interpret data, and to articulate the clinical significance of all adverse events. The NCI-CTCAE manual has been reviewed by the Protocol Chair, ITN Clinical Trial Physician and NIAID Medical Monitor and has been deemed appropriate for the participant population to be studied in this protocol.

Adverse events will be graded on a scale from 1 to 5 according to the following standards in the NCI-CTCAE manual:

Grade 1 = mild adverse event.

Grade 2 = moderate adverse event.

Grade 3 = severe adverse event.

Grade 4 = life-threatening or disabling adverse event.

Grade 5 = death.

For grading an abnormal value or result of a clinical or laboratory evaluation (including, but not limited to, a radiograph, an ultrasound, an electrocardiogram etc.), a treatment-emergent adverse event is defined as an increase in grade from baseline or from the last post-baseline value that doesn't meet grading criteria. Changes in grade from screening to baseline will also be recorded as adverse events, but are not treatment-emergent. If a specific event or result from a given clinical or laboratory evaluation is not included in the NCI-CTCAE manual, then an abnormal result would be considered an adverse event if changes in therapy or monitoring are implemented as a result of the event/result.

For additional information and a printable version of the NCI-CTCAE manual, consult the NCI-CTCAE web site:

https://ctep.cancer.gov/protocoldevelopment/electronic applications/ctc.htm#ctc 50.

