#### 12.8.2.2 Ad hoc DSMB Reviews

In addition to the pre-scheduled data reviews and planned safety monitoring, the DSMB may be called upon for *ad hoc* reviews. The DSMB will review any event that potentially impacts safety at the request of the protocol chair or DAIT/NIAID. In addition, the following events will trigger an *ad hoc* comprehensive DSMB Safety Review:

- Any death that occurs in the study, which is possibly related or related to study medication (Table 4).
- The occurrence of a Grade 3 or higher SAE related to study treatment that is also a SUSAR in one or more of the study participants who have received study treatment.
- Any occurrence of a Grade 3 or higher anaphylaxis reaction (Table 3).
- Two or more events of skin malignancy in individuals who receive nbUVB during the study.

The DSMB will review the data within 2 weeks of the event being identified. If the DSMB has not reviewed the data within 2 weeks, study enrollment, as defined in Section 8.1, will be suspended and no additional participants will sign consent. Participants already in screening may continue with screening assessments, and participants already enrolled in the trial will continue as planned, pending completion of the DSMB *ad hoc* review. After review of the data, the DSMB will make recommendations regarding study conduct and/or continuation.

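### The protocol does not settle which scale grades local and skin-only reactions, and a skin-only reaction labelled hypersensitivity must go on Table 3, which shows no skin sign above Grade 1

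*Combined protocol and SAP*

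**What the plan says.** Section 12.3.1 states, without an alternative, that "hypersensitivity and anaphylaxis reactions will be graded according to Table 3 below". It gives the source of the table as "Modified from World Allergy Organization Subcutaneous Immunotherapy Systemic Reaction Grading System". Grade 1 in Table 3 is "Symptom(s)/ sign(s) of one organ system". Grade 2 begins "Symptom(s)/ sign(s) of more than one Grade 1 organ system present or" and goes on to lower-airway, gastrointestinal or uterine signs. Grades 3 and 4 list only respiratory and cardiovascular signs, and Grade 5 is death.

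Section 12.3.3 assigns NCI-CTCAE v5.0 to the remainder: "For all other adverse events not related to hypersensitivity, anaphylaxis or liver chemistry abnormalities".

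Section 12 does not define which events count as hypersensitivity. Section 5.1 comes closest: "Hypersensitivity events such as injection site reaction (13.3%), injection site pain (2%), rash (4.7%), and eczema (3.1" (the last figure is 3.1%). It adds that all of these were mild and transient. The monitoring sentence later in Section 5.1 names injection-site reaction as an item apart from hypersensitivity. So does Section 6.1.3.3, where participants are watched "to detect any possible injection site reaction, hypersensitivity, and/or anaphylaxis". Section 5.4 lists injection-site reactions as a risk of drug administration.

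The grade then feeds several rules:

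- Section 12.4.3: eCRF recording from Grade 2, plus serious events, Grade 1 generalized pruritus or urticaria, and confirmed Grade 1 SARS-CoV-2 infection.
- Section 3.3.2: the first safety endpoint counts Grade 2 or higher AEs.
- Section 6.1.3.4: dosing stops for Grade 2 or higher reactions and for Grade 1 generalized pruritus or urticaria.
- Section 6.5, item 1: permanent discontinuation for a related AE of Grade 3 or more.
- Section 12.8.2.2: ad hoc DSMB review for "The occurrence of a Grade 3 or higher SAE related to study treatment that is also a SUSAR", and for Grade 3 or higher anaphylaxis on Table 3.

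**The concern.** Table 3 comes from a scale for systemic reactions. It ranks a reaction by how many and which organ systems are involved, not by how bad the reaction is within one system. For anaphylaxis that is sensible. For a reaction confined to the skin it leaves nowhere to go above Grade 1.

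The label therefore changes the grade. A severe rash that the site does not attribute to hypersensitivity goes to CTCAE and can be graded on its severity. The same rash called hypersensitivity goes to Table 3 and is Grade 1. Attributing a rash to drug allergy thus makes it less likely to be recorded and counted.

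The protocol also uses the word hypersensitivity in two ways, and the synopsis plans 5 to 10 sites. Two sites could grade the same local reaction on different scales, both in good faith. The Grade 2 or higher endpoint, and the AE incidence compared by Fisher's exact test in Section 13.4.4, would then depend partly on site labelling.

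**Working it through.** **Step 1. Trace one event through the rules.** Take a moderate or severe non-urticarial rash or eczema, confined to the skin and labelled hypersensitivity.

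1. Section 12.3.1 sends it to Table 3, and Section 12.3.3 excludes it from CTCAE.
2. One organ system is involved, so it is Grade 1. Grade 2 needs a second organ system or a lower-airway, gut or uterine sign, and the event has none. Grades 3 and 4 contain no skin entry.
3. Section 6.1.3.4 agrees with this reading: it describes even generalized pruritus or urticaria as Grade 1.

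**Step 2. Apply each rule to that Grade 1 event.**

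| Rule | Rash or eczema, Grade 1 | Generalized pruritus or urticaria, Grade 1 |
|---|---|---|
| eCRF recording, 12.4.3 | No, unless serious | Yes |
| Safety endpoint 1, 3.3.2 | Not counted | Not counted |
| Dosing stop, 6.1.3.4 | Not listed | Listed |
| Related Grade 3 AE, 6.5 item 1 | Not met | Not met |
| Grade 3 limbs, 12.8.2.2 | Not met | Not met |

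Section 6.5 item 5 names no grade, but it cites Section 6.4.1, which leads back to the list in Section 6.1.3.4.

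**Step 3. Check the Section 5.1 rates and scale them.** Section 5.1 gives no denominator. The 256 individuals treated with AMG 714 (Section 1.4.1) are assumed. The trial's AMG 714 arm is 57 × 2/3 = 38.

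| Event | Count assumed | Count / 256 | Stated | Expected in 38 |
|---|---|---|---|---|
| Injection-site reaction | 34 | 13.28% | 13.3% | 5.05 |
| Injection-site pain | 5 | 1.95% | 2% | 0.74 |
| Rash | 12 | 4.69% | 4.7% | 1.78 |
| Eczema | 8 | 3.13% | 3.1% | 1.19 |

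All four stated rates are reproduced by whole-number counts over 256.

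**Step 4. Size the exposed group.** Rash plus eczema is 4.7% + 3.1% = 7.8%. In 38 participants that is 1.78 + 1.19 = 2.97, or about 3.0, of any severity and if no one has both.

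The documents give no rate of moderate or severe events. If the share is anywhere from 0 to 25% (an assumption), the number lost from safety endpoint 1 is 0 to 0.25 × 2.97 = 0.74, or 0 to about 0.7 participants.

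**The case against.** **Section 5.1 is background, not a grading rule.** It summarises the Investigator's Brochure, and Section 12 does not cite it to define what belongs on Table 3. A reader might infer that all four event types in Section 5.1 are certain to be graded on Table 3. That would make the exposed group 5.05 + 0.74 + 1.78 + 1.19 = 8.8 of 38. The documents do not support this for injection-site events: Sections 5.1 (monitoring sentence), 5.4 and 6.1.3.3 treat them separately, and Table 3 shows no local-reaction entry. This part of the objection stands, so the injection-site events are left out of the size estimate. For rash and eczema no section points the other way, and Sections 12.3.1 and 12.3.3 leave the site no choice once the label is applied.

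**Other rules catch what matters.** Generalized pruritus or urticaria is recorded and stops treatment at Grade 1, and ends it permanently under Section 6.4.1. Any AE judged significant suspends treatment (Section 6.4). Section 6.5 item 8 allows discontinuation on judgement. All serious events, including important medical events, are reported within 24 hours (Sections 12.2.3 and 12.5.1). This also stands as regards participant safety. It does not restore the lost count in safety endpoint 1, or the eCRF record of a non-serious event.

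**Section 8.3.1 says that all AEs are recorded on case report forms.** It does so by reference to Section 12, where Section 12.4.3 sets the Grade 2 threshold. Lower grades are kept in source documents only (Section 12.4.2).

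**The table text is incomplete.** As extracted, the Grade 1 cell begins at angioedema and seems to have lost its skin entries, so the printed table should be checked. The cap rests on the Grade 2 to 5 cells, which show no skin item.

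**Earlier events were all mild.** That stands, and it is why the expected effect is small.

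**Conclusion.** The point holds as a grading gap with a small expected effect. The sections do not settle which scale grades local and skin-only reactions. As written, a moderate or severe non-urticarial rash or eczema labelled hypersensitivity is Grade 1, with the losses shown in the table of rules. Generalized pruritus or urticaria escapes most of this but still cannot count as Grade 2 or higher in the endpoint.

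The size is about 3.0 of 38 AMG 714 participants with rash or eczema of any severity, and 0 to about 0.7 lost from the endpoint. This assumes a denominator of 256, rates that carry over to vitiligo, no overlap between the two events, and a moderate-or-worse share of 0 to 25%.

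Two stronger readings are not supported:

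- *The AE comparison is biased toward no difference.* The documents give no placebo rates for these events. Placebo has the same excipients and is also given as two 1.5 mL injections (Sections 6.1.2 and 6.1.3.1). The direction of any bias is not shown.
- *A severe skin reaction such as Stevens-Johnson Syndrome would escape oversight.* Section 12.5.2.2 names it as an event where one case can support a causal link. As a SUSAR it would go to the FDA, and the DSMB is told of expedited reports (Section 12.8.2.1). What could be missed is one automatic ad hoc trigger, and only if the event were labelled hypersensitivity and graded below 3 on Table 3.

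**What to change.** 1. Reconcile Sections 5.1, 6.1.3.3, 12.3.1 and 12.3.3 so that each local or skin-only reaction has one defined grading path.
2. For any local or skin-only reaction graded on Table 3, also record its CTCAE v5.0 grade. Section 12.3.3 already adopts that scale for other AEs.
3. State that the higher of the two grades decides eCRF recording under Section 12.4.3 and inclusion in safety endpoint 1. It must apply to the recording threshold as well, or the event never reaches the database.
4. State which grade feeds the rules in Sections 6.1.3.4, 6.5 and 12.8.2.2. The clinical team must reconcile this; no clinical rule is proposed here.

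The cost is a few sentences, one more grade field on the eCRF, and a few more recorded AEs.

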# 12.3.2 Grading of Liver Chemistry Abnormalities

For this study, liver function abnormalities will be graded using protocol specific criteria, and are defined relative to the upper limit of normal (ULN) as follows:

- Aspartate aminotransferase [AST] increased
  - o Grade 1: > ULN 3.0x ULN
  - $\circ$  Grade 2: > 3.0x ULN 5.0x ULN
  - o Grade 3: > 5.0x ULN 20.0x ULN
  - $\circ$  Grade 4: > 20.0x ULN
- Alanine aminotransferase [ALT] increased

- o Grade 1: > ULN 3.0x ULN
- $\circ$  Grade 2: > 3.0x ULN 5.0x ULN
- o Grade 3: > 5.0x ULN 20.0x ULN
- o Grade 4: > 20.0x ULN
- Alkaline phosphatase [ALP] increased
  - o Grade 1: > ULN 2.5x ULN
  - o Grade 2: > 2.5x ULN 5.0x ULN
  - o Grade 3: > 5.0x ULN 20.0x ULN
  - $\circ$  Grade 4: > 20.0x ULN
- Blood bilirubin increased
  - o Grade 1: > ULN 1.5x ULN
  - o Grade 2: > 1.5x ULN 3.0x ULN
  - o Grade 3: > 3.0x ULN 10.0x ULN
  - o Grade 4: > 10.0x ULN

#### 12.3.3 Grading Criteria

For all other adverse events not related to hypersensitivity, anaphylaxis or liver chemistry abnormalities, the study site will grade the severity of adverse events experienced by the study participants according to the criteria set forth in the NCI-CTCAE (version 5.0, November 27, 2017). This document (here in referred to as the NCI-CTCAE manual) provides a common language to describe levels of severity, to analyze and interpret data, and to articulate the clinical significance of all adverse events. The NCI-CTCAE manual has been reviewed by the Protocol Chair, ITN Clinical Trial Physician and NIAID Medical Monitor and has been deemed appropriate for the participant population to be studied in this protocol.

Adverse events will be graded on a scale from 1 to 5 according to the following standards in the NCI-CTCAE manual:

Grade 1 = mild adverse event.

Grade 2 = moderate adverse event.

Grade 3 = severe adverse event.

Grade 4 = life-threatening or disabling adverse event.

Grade 5 = death.

For grading an abnormal value or result of a clinical or laboratory evaluation (including, but not limited to, a radiograph, an ultrasound, an electrocardiogram etc.), a treatment-emergent adverse event is defined as an increase in grade from baseline or from the last post-baseline value that doesn't meet grading criteria. Changes in grade from screening to baseline will also be recorded as adverse events, but are not treatment-emergent. If a specific event or result from a given clinical or laboratory evaluation is not included in the NCI-CTCAE manual, then an abnormal result would be considered an adverse event if changes in therapy or monitoring are implemented as a result of the event/result.

For additional information and a printable version of the NCI-CTCAE manual, consult the NCI-CTCAE web site:

https://ctep.cancer.gov/protocoldevelopment/electronic applications/ctc.htm#ctc 50.

#### 12.3.4 Attribution Definitions

The relationship, or attribution, of an adverse event to the study drug or study procedure(s) will initially be determined by the site investigator and recorded on the appropriate AE/SAE eCRF. Final determination of attribution for safety reporting will be determined by DAIT/NIAID. The relationship of an adverse event to study drug or procedures will be determined using the descriptors and definitions provided in Table 4.

Table 4. Attribution of Adverse Events

Code	Descriptor	Relationship (to primary investigational drug and/or other concurrent mandated study drug or study procedure)						
Unrelated Category								
1 Not Related The adverse event is clearly not related: there is in evidence to suggest a causal relationship.								
Related C	ategories							
7		The adverse event has a reasonable possibility to be related; there is evidence to suggest a causal relationship.						
3	Related	The adverse event is clearly related.						

#### 12.4 COLLECTION AND RECORDING OF ADVERSE EVENTS

#### 12.4.1 Collection Period

All adverse events will be collected from the time the participant signs the informed consent until the participant completes study participation or until 30 days after he/she prematurely withdraws (without withdrawing consent) or is withdrawn from the study.

#### 12.4.2 Collecting Adverse Events

Details regarding all AEs and SAEs will be collected in the source documents. Adverse events (including SAEs) may be discovered through any of these methods:

- Observing the participant
- Interviewing the participant
- Receiving an unsolicited complaint from the participant
- In addition, an abnormal value or result from a clinical or laboratory evaluation can also indicate an adverse event, as defined in Section 12.3.

#### 12.4.3 Recording Adverse Events

Grade 2 or higher AEs will be recorded on the appropriate AE case report form (eCRF) for this study. A generalized pruritus or urticaria Grade 1 hypersensitivity/anaphylaxis reaction,

or confirmed Grade 1 SARS-CoV-2 infection will also be recorded (Section 6.1.3.4). The investigator will record these adverse events and serious adverse events (Section 12.2) on the appropriate AE/SAE eCRF regardless of the relationship to study treatment or study procedure.

Once recorded, an AE/SAE will be followed until it resolves with or without sequelae, or until the end of study participation, or until 30 days after the participant prematurely withdraws (without withdrawing consent) or is withdrawn from the study, whichever occurs first.

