#### 1.4 CLINICAL STUDIES

## 1.4.1 Safety Data for AMG 714

According to the current version of the AMG 714 Investigator's Brochure (IB), 256 individuals have received AMG 714, including 200 individuals who were dosed biweekly for 12 weeks. These individuals participated in six completed clinical trials in healthy participants and participants with psoriasis, rheumatoid arthritis, celiac disease, and refractory celiac disease. In these six trials, treatment-emergent adverse events (TEAEs) were reported in 190 (74.2%) individuals receiving AMG 714 and in 70 (64.8%) individuals receiving placebo. Most TEAEs were non-serious and were mild to moderate in severity. Nineteen serious adverse events (SAEs) were reported, of which 15 occurred in individuals receiving

AMG 714. These SAEs included sepsis and deep vein thrombosis (80 mg AMG 714); hip fracture, nerve compression, C5-C6 nerve compression, and asthma (280 mg AMG 714); flare of rheumatoid arthritis (0.15 mg/kg single dose AMG 714 SQ); and peroneal nerve palsy, hepatitis, tuberculosis, pneumococcal infection, balance disorder and cerebellar syndrome (8 mg/kg AMG 714). None of these SAEs was assessed as related to AMG 714.

Injection site reactions were the most commonly reported adverse event. No injection reactions were classified as an SAE. No deaths and no anaphylaxis events were reported in individuals treated with AMG 714.

Anti-AMG 714 antibodies were detected in 8 of the 256 individuals treated with AMG 714 and in 1 individual receiving placebo. Anti-drug antibodies (ADAs) were detected in 4 of the 8 subjects before receiving any dose of AMG 714. Neutralizing antibodies were observed in 1 subject who received a single dose of AMG 714. There were no effects on pharmacokinetics in any subject with detectable ADAs. The presence of ADAs does not appear to be associated with increased risk of adverse events or laboratory abnormalities.

In summary, AMG 714 was well tolerated in the completed clinical trials and has demonstrated an acceptable safety profile.

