### 2.3 SECONDARY OBJECTIVES

The secondary objectives are to:

- 1. Evaluate the safety and tolerability of AMG 714 in vitiligo.
- 2. Determine the efficacy of IL-15 inhibition with AMG 714 at inducing total body skin repigmentation in vitiligo.
- 3. Assess the durability of the skin repigmentation achieved by AMG 714 in vitiligo.
- 4. Evaluate the efficacy of AMG 714 followed by narrow band UVB (nbUVB) phototherapy.

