#### 8.3.1 General Assessments

- Informed consent: Written informed consent will be obtained before any study assessments or procedures are performed
- Eligibility criteria: Eligibility for study participation will be assessed during the screening period
- Demographics: Age, sex, and ethnicity
- Medical history: A history will be taken to determine if the participant has had any clinically significant diseases or medical procedures other than the disease under study
- Vital signs: Height will be obtained at screening (V-1); weight, temperature, pulse, blood pressure, and respiration will be obtained at all visits
- Comprehensive physical examination includes the following body systems: Skin, respiratory, cardiovascular, gastrointestinal, neurologic, and renal/urinary
- Limited physical examination includes the skin and focuses on the body systems relevant to the participant's clinical complaints and clinical status at the study visit
- Vitiligo history, including date of diagnosis, type (active or stable), and previous treatments
- Adverse events: Participants will be assessed for AEs. All adverse events will be graded, recorded on the case report forms (CRFs), and reported per Section 12
- Concomitant medications: All concomitant medications and their indications for use will be recorded
- Treatment Assignment Survey (Appendix 6)

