# 12.5.2.1 Annual Reporting

DAIT/NIAID will include in the annual study report to health authorities all adverse events classified as:

• Serious, expected, suspected adverse reactions (Section 12.2.1.1)

- Serious and not a suspected adverse reaction (Section 12.2.2)
- Pregnancies.

Note that all adverse events (not just those requiring 24-hour reporting) will be reported in the Annual IND Report.

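### Section 12.4.3 keeps Grade 1 injection-site reactions off the eCRF, so low-grade local tolerability cannot be described by arm, and the AE grade rules in Sections 8.3.1, 12.4.3 and 13.4.4 need to be aligned

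*Combined protocol and SAP*

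**What the plan says.** **Recording rule.** Section 12.4.3: "Grade 2 or higher AEs will be recorded on the appropriate AE case report form (eCRF) for this study". Two Grade 1 exceptions follow: "A generalized pruritus or urticaria Grade 1 hypersensitivity/anaphylaxis reaction", "or confirmed Grade 1 SARS-CoV-2 infection will also be recorded". SAEs are recorded as well. Section 12.4.2 has details of AEs of every grade collected in source documents.

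**A second rule.** Section 8.3.1, on the assessments at study visits: "All adverse events will be graded, recorded on the case report forms (CRFs), and reported per Section 12".

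**Objective, endpoint and analysis.** Secondary objective 1 (Section 2.3) is "Evaluate the safety and tolerability of AMG 714 in vitiligo". The first safety endpoint (Section 3.3.2) is Grade 2 or higher AEs. Section 13.4.4 compares AE incidence between arms over the first 24 weeks by Fisher's exact test and gives no grade for it.

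**Known reactions.** Section 1.4.1: "Injection site reactions were the most commonly reported adverse event". Section 5.1 lists injection site reaction (13.3%), rash (4.7%), eczema (3.1%) and injection site pain (2%) as hypersensitivity events on AMG 714, and adds: "All hypersensitivity reactions were mild and transient". Section 12.3.3 equates Grade 1 with mild.

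**The concern.** The objective names tolerability as well as safety. The local reaction that a subcutaneous antibody is most likely to cause is, on the protocol's own account, common and mild. A Grade 2 floor on the eCRF therefore removes most or all of these reactions from the data that will be analysed. Yet Sections 5.1 and 6.1.3.3 require an hour of observation after every dose, partly to detect them. The observation is made and written in the source documents, and then goes no further. The monthly reports to the Medical Monitor (Section 12.8.1) are also built from eCRF entries.

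The second issue is consistency. Section 8.3.1 and Section 12.4.3 give different recording rules, and Section 13.4.4 does not say which grades enter its comparison. As it stands, the recorded AEs would be a mixture of Grade 2 or higher events and two kinds of Grade 1 event. That is neither an all-grade incidence nor the endpoint in Section 3.3.2.

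**Working it through.** **Inputs**
- AMG 714 arm: 57 randomized 2:1 (Section 3.1), so 57 × 2/3 = 38, with 19 on placebo.
- Prior exposure: 256 individuals (Section 1.4.1).
- Reaction rates: Section 5.1, as above.
- Mild = Grade 1: Section 12.3.3. Section 5.1 names no grading scale, so applying this equivalence to its figures is an inference.

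**The protocol's own figures.** The overall TEAE rate on AMG 714 reproduces: 190/256 = 74.2%. Section 5.1 gives no denominator, but 256 fits: 34/256 = 13.3%, 12/256 = 4.7%, 8/256 = 3.1%, 5/256 = 2.0%.

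**Step 1: reactions expected among 38 on AMG 714**
- Injection site reaction: 38 × 0.133 = 5.05. Chance of at least one: 1 − (1 − 0.133)^38 = 0.996.
- Rash: 38 × 0.047 = 1.8. Eczema: 38 × 0.031 = 1.2. Injection site pain: 38 × 0.02 = 0.8.

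**Step 2: injection-site reactions that reach the eCRF under Section 12.4.3**
- If all are mild, as Section 5.1 says: 0.
- Allowing for sampling error in 0 Grade 2 or higher among 256: the one-sided 95% upper limit is 1 − 0.05^(1/256) = 1.16%, and 38 × 0.0116 = 0.44.
- If 10 to 30% were Grade 2 or higher (an assumption): 38 × 0.133 × 0.10 = 0.5, up to 38 × 0.133 × 0.30 = 1.5.

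So about 5 expected reactions become about 0 in the analysis data, and at most 1 or 2 on the less favourable assumption.

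**Step 3: what full recording would support.** The documents give no placebo rate for injection-site reactions. With assumed placebo rates of 0%, 5% and 10%, exact power of the two-sided Fisher test (38 v 19, α = 0.05) against 13.3% is 12.4%, 5.1% and 2.8%. The result would be a description by arm, not a test.

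**Step 4: the rules side by side**

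| Section | AEs covered |
|---|---|
| 3.3.2 (endpoint) | Grade 2 or higher |
| 8.3.1 (CRFs) | All |
| 12.4.2 (source documents) | All |
| 12.4.3 (eCRF) | Grade 2 or higher, two Grade 1 exceptions, SAEs |
| 13.4.4 (comparison) | No grade stated |

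Sections 3.3.2 and 12.4.3 fit together, and 12.4.2 concerns source documents, so it conflicts with neither. Section 8.3.1 differs from 12.4.3, and 13.4.4 leaves its grade open.

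**The case against.** The best defence is that the threshold was chosen to match the endpoint. Section 3.3.2 defines the safety endpoint as Grade 2 or higher AEs, and Section 12.4.3 records what that endpoint needs. This stands. A reader might infer that the tolerability objective cannot be answered at all; the documents do not support that. Grade 2 or higher AEs, SAEs, Grade 1 generalized pruritus or urticaria, and hypersensitivity reactions that end treatment (reported within 24 hours under Section 12.5.1) are all captured. Section 1.4.1 describes most earlier TEAEs as mild to moderate, so some Grade 2 events should be expected.

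A reader might also argue that 0/38, with a one-sided 95% upper limit of 1 − 0.05^(1/38) = 7.6%, would falsely exclude the 13.3% in Section 5.1. It would not. A recorded 0/38 is a Grade 2 or higher count and says nothing about the all-grade rate. No section plans such an interval.

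The 13.3% is itself soft. It pools studies with single and repeated doses, different dose levels, and both subcutaneous and intravenous use.

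On consistency, the sentence in Section 8.3.1 ends by pointing to Section 12, so Section 12.4.3 can be read as the governing rule. That different sites would follow different rules is possible but not shown. Two further supposed conflicts are weak. Section 12.4.1 concerns collection, not eCRF entry. Section 12.5.2.1 ("Note that all adverse events (not just those requiring 24-hour reporting) will be reported in the Annual IND Report") contrasts with events needing 24-hour reporting, not with a grade, and concerns what the sponsor reports.

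What the defence does not meet is that the objective names tolerability, that the commonest known reaction falls below the threshold on the protocol's own evidence, and that Sections 8.3.1 and 13.4.4 still do not match 12.4.3.

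**Conclusion.** The point holds for low-grade local tolerability and for the consistency of the AE rules. Moderate and severe safety is adequately covered. At the 13.3% in Section 5.1, about 5 of 38 AMG 714 participants would be expected to have an injection-site reaction and about 0 would be available for analysis (0.5 to 1.5 if 10 to 30% were Grade 2 or higher).

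This rests on three assumptions: that the pooled earlier rate carries over to this regimen and population, that mild in Section 5.1 corresponds to Grade 1 in Section 12.3.3, and that sites follow Section 12.4.3 rather than 8.3.1. The mismatch between the sections needs none of these assumptions. Neither the primary analysis nor the sample size is affected.

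**What to change.** 1. In Section 12.4.3, add Grade 1 injection-site reactions to the existing Grade 1 exceptions, and in Section 13.4 report their incidence by arm descriptively. Do not extend this to every Grade 1 symptom in Table 3. That list includes rhinitis, cough, nausea and headache, which would burden sites, and as shown it contains no local injection-site reaction.
2. Reconcile Sections 8.3.1 and 12.4.3 so that both state one recording threshold.
3. In Section 13.4.4, state that the AE incidence compared between arms is Grade 2 or higher, to match Section 3.3.2. The Grade 1 exceptions then stay out of that comparison.

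The cost is amendment wording, a few more eCRF entries (about 5 AMG 714 participants with a reaction at the 13.3% rate, plus any on placebo) and a slightly higher reported AE count. No visit or procedure is added, because the post-dose observation and the source documentation are already required. The by-arm figures would be descriptive, with power of only about 3 to 12% under the assumed placebo rates.
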